### **Nonserious Adverse Event Collection and Reporting**

The collection of nonserious AE information will begin at initiation of study.

All nonserious adverse events (not only those deemed to be treatment-related) should be collected during the treatment period for a minimum of 365 days following the procedure.

### **Serious Adverse Event Collection and Reporting**

Following the subject's written consent to participate in the study, all SAEs, whether related or not related to study drug, must be collected. All SAEs must be collected that occur within 365 days after procedure.

SAEs, whether related or not related to study procedure, and pregnancies must be reported. SAEs must be recorded an approved form; SAE report should be sent within 24 hours.

Assessment of Myocardial Ischemic-Reperfusion Injury During Off- and On- Pump CABG (ClinicalTrials.gov Identifier: NCT03050489). Corresponding author: [name] [[contact]](mailto:[contact]) [contact]

Date of the document 06 December 2016

### **Pregnancy**

There will be no pregnancy cases.

### **Other Safety Considerations**

Any significant worsening noted during interim or final physical examinations, electrocardiograms, x-rays, and any other potential safety assessments, whether or not these procedures are required by the protocol, should also be recorded as a nonserious or serious AE, as appropriate, and reported accordingly.

### **ETHICAL CONSIDERATIONS. INFORMED CONSENT**

This study will be conducted in accordance with International Society for Pharmacoepidemiology (ISPE) Guidelines for Good Pharmacoepidemiology Practices (GPP), in accordance with Good Clinical Practice (GCP), as defined by the International Conference on Harmonisation (ICH) and in accordance with the ethical principles the Declaration of Helsinki of 2000, Russian version – September 20, 2002.

The study will also be carried out in keeping with federal, state, and local laws, rules and regulations.

The study will be conducted in compliance with the protocol. The protocol, any amendments, and the subject informed consent will receive Institutional Review Board/Independent Ethics Committee (IRB/IEC) approval/favorable opinion before initiation of the study.

Investigators must ensure that subjects are clearly and fully informed about the purpose of the study in which they participate. Freely given written informed consent must be obtained from every subject before participation in the study and the Informed Consent Form (APPENDIX 1) should be signed. Two copies of the Informed Consent Form will be signed by the patient. One copy of the Informed Consent Form will be taken by the patient; another remains with the investigator and is placed in the records. The rights, safety, and well-being of the study subjects are the most important considerations and should prevail over interests of science and society.

All subject names will be kept confidential. Subjects will be identified throughout documentation and evaluation by the Individual Identification code allotted to them during the study. The subjects will be told that all study findings will be handled in strictest confidence.

### **DATA ANALYSIS**

#### **Sample Size Justification**

Since it is exploratory study and no statistical hypotheses will be tested, sample size calculation was not conducted for this study. Thus, about 300 patients is planned to be included in the analysis.

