Title	Assessment of Myocardial Ischemic-Reperfusion Injury During Off- and On- Pump CABG (AMIRI-CABG) ClinicalTrials.gov Identifier: NCT03050489	
Authors *	[name]	
Trial design	Prospective non-randomized single center	
Methods		
Participants	Eligibility criteria: multivessel coronary artery disease with indications for elective coronary artery bypass grafting	
Interventions	Group 1: off-pump CABG Group 2: on-pump CABG Group 3: pump-assisted CABG (on-pump CABG without aortic cross-clamping)	
Objective	To compare level of MPO between three groups of intervention	
Primary objective	To compare ischemic-reperfusion injury between three groups of intervention	

Assessment of Myocardial Ischemic-Reperfusion Injury During Off- and On- Pump CABG  
 (ClinicalTrials.gov Identifier: NCT03050489). Corresponding author: [name]  
[[contact]](mailto:[contact]) [contact]

Date of the document 06 December 2016

Secondary objective	To assess ability of MPO to predict worse outcome (death) To assess relation between MPO and TnI	
Outcome	MPO level after CABG, death after CABG	
Randomization	Non-randomized allocation. Heart Team decision.	
Blinding (masking)	None	
Results		
Numbers randomized	Number of participants screened n=500  Allocated (non-randomized): off-pump CABG (n=181), on-pump CABG (n=128), pump-assisted CABG (n=27)	
Recruitment	Complete	
Numbers analyzed	Off-pump CABG: 181 On-pump CABG: 128 Pump-assisted CABG: 27	
Outcome	Could MPO predict death during 30 days after CABG	
Harms	Important adverse events or side effects	
Conclusions	CPB activates leucocytes that cause myocardial damage  Preoperative MPO level could evaluated as a predictor of myocardial damage and worse outcome after CABG	
Trial registration	ClinicalTrials.gov Identifier: NCT03050489	
Funding	Assessment of regenerative ability after cardiac surgery	

*Table 2 Statistical analysis synopsis*

Assessment of Myocardial Ischemic-Reperfusion Injury During Off- and On- Pump CABG ClinicalTrials.gov Identifier: NCT03050489	
Hypothesis	Ischemic – reperfusion injury are comparable between groups
Primary objective	To compare ischemic-reperfusion injury during off-pump, on-pump and pump – assisted CABG
Secondary objective	To assess ability of myeloperoxidase to predict worse outcome after CABG

Assessment of Myocardial Ischemic-Reperfusion Injury During Off- and On- Pump CABG  
 (ClinicalTrials.gov Identifier: NCT03050489). Corresponding author: [name]  

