[[contact]](mailto:[contact]) [contact]

Date of the document 06 December 2016

Type of trial	Prospective non-randomised single-centre
Type of research	Exploratory
Timeline	2015-2019
Groups	Off-pump  On – pump  Pump-assisted (on-pump without aortic cross-clamping)
Sample size estimation	> 300 patients
Planned sample size	Average: 300  Off-pump: 100  On-pump: 100  Pump-assisted: 100
Actual sample size	Average: 336  Off-pump: 181 (conversion 6)  On-pump: 128  Pump-assisted: 27
Baseline characteristics comparing	Testing for type of distribution of baseline characteristics:  ANOVA for normal distribution  Kruskal-Wallis test with multiple groups comparison adjustment for non-normal distribution  Chi-squared test or exact Fisher's test for nominal data
Statistics hypothesis testing	ANOVA/ANCOVA for MPO level, troponin I level
Missing Data Handling	Drop observations with missing data
Evaluating of reason of missingness	Hypothesis: Missing data depend on severity of complications  Hypothesis testing with logistic regression model: Missingness = complications

Assessment of Myocardial Ischemic-Reperfusion Injury During Off- and On- Pump CABG  
(ClinicalTrials.gov Identifier: NCT03050489). Corresponding author: [name]  
[[contact]](mailto:[contact]) [contact]

Date of the document 06 December 2016

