### Primary endpoint analysis

Hypothesis: MPO levels after procedure are different between groups.

Hypothesis testing:

- Normality test (Kolmogorov-Smirnov test, Shapiro-Wilk test)

Group comparing:

Continuous variables

- Non-normal distribution: Kruskal-Wallis test with adjustment for multiple comparisons

*Table 6 Myeloperoxidase variables specifications*

Characteristic	Variable name in database	Test
MPO level before procedure	MPOPreOp	Kruskal-Wallis test
MPO level after procedure	MPOPostOp	Kruskal-Wallis test

*Table 7 Myeloperoxidase before and during coronary artery bypass grafting (CABG)*

Variables	off-pump CABG (N=181)	on-pump CABG (N=128)	pump-assisted CABG (N=27)	P Value*
MPO before CABG				0.2904
Nmiss (%)	34 (18.8)	21 (16.4)	9 (33.3)	
Mean±SD	35.8±32.1	39.9±30.6	29.2±14.8	
Min–Max	2.8–237.8	4.0–168.9	5.6–65.4	
Median (IQR)	27.7 (17.0–41.0)	31.0 (19.0–48.7)	29.0 (18.7–34.0)	
MPO after CABG				<.0001
Nmiss (%)	28 (15.5)	26 (20.3)	13 (48.1)	

Date of the document 06 December 2016

Variables	off-pump CABG (N=181)	on-pump CABG (N=128)	pump-assisted CABG (N=27)	P Value*
Mean±SD	96.2±75.3	210.9±138.7	175.0±102.6	
Min–Max	9.1–410.3	16.7–824.6	63.4–374.5	
Median (IQR)	66.5 (41.3–135.8)	184.3 (135.0–250.0)	144.7 (95.0–284.9)	

\* Kruskal-Wallis test, Nmiss – number of missing values, SD – standard deviation, IQR – interquartile range, CABG – coronary artery bypass grafting

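### The reason given for omitting a sample size calculation is contradicted by the tests the plan runs, and pump-assisted CABG reached 27 of 100 planned patients, 14 of them with the primary endpoint

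*Combined protocol and SAP*

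**What the plan says.** The combined protocol and SAP gives its whole case for the sample size in two sentences under Sample Size Justification: "Since it is exploratory study and no statistical hypotheses will be tested, sample size calculation was not conducted for this study", followed by the statement that "about 300 patients is planned to be included in the analysis". The synopsis (Table 2) words the estimate as "> 300 patients" and splits the plan equally over three techniques, including "Pump-assisted: 100". Its line for the actual size reads "Pump-assisted: 27". Table 3 repeats both sets of numbers, and the text below it reports 6 conversions from off-pump, so that 33 pump-assisted procedures were performed.

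The analysis sections are built on hypotheses. Primary endpoint analysis opens with "Hypothesis: MPO levels after procedure are different between groups" and reports a Kruskal-Wallis p-value. The synopsis carries its own hypothesis, "Ischemic – reperfusion injury are comparable between groups", and has a row for hypothesis testing by ANOVA/ANCOVA.

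**The concern.** The document gives two reasons for having no calculation: that the study is exploratory and that nothing will be tested. The first may be defended; the second is not true of this plan. Once it is removed, the reader has no account of what the chosen size can and cannot show.

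That matters most for the smallest group. A total near 300 suggests a balanced three-way comparison, but the overall count says nothing about precision in a group that fell far short. The risk is that a non-significant result involving pump-assisted CABG is read as similarity or as absence of a relationship. The document already contains one such reading, in the troponin analysis for that group.

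**Working it through.** **1. The reason against the analyses.** Sample Size Justification says "no statistical hypotheses will be tested, sample size calculation was not conducted for this study". Hypotheses are stated, and tests or p-values given, in:
- the synopsis (Table 2);
- Baseline Characteristics;
- Primary endpoint analysis;
- the ANCOVA sections for MPO and troponin I;
- the logistic model for death;
- the missingness model.

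The Secondary Endpoint Analysis tables also carry p-values throughout.

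**2. The planned figure.** 3 × 100 = 300, so the planned numbers add up. No alpha, power, effect size, SD or dropout rate is given, so 300 cannot be reproduced or refuted.

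**3. Delivered numbers (Tables 2 and 3).**
- Total: 181 + 128 + 27 = 336.
- Excess in the other two groups: 81 + 28 = 109. Pump-assisted shortfall: 100 - 27 = 73. Net: 109 - 73 = 36 above 300.
- By procedure performed: 27 + 6 = 33, a shortfall of 67. The performed counts in Table 3 sum to 175 + 127 + 33 = 335, not 336.

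**4. Primary endpoint observed (Tables 7 and 25).** 181 - 28 = 153; 128 - 26 = 102; 27 - 13 = 14. The document does not say how many of the 33 performed have post-operative MPO.

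**5. Precision.** Half-width of a 95% interval in SD units = 1.96 × √(1/n₁ + 1/n₂). Assumptions, none stated in the plan: two-sided 0.05, common SD, normal approximation.

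| Basis | n₁ v n₂ | Half-width (SD) |
|---|---|---|
| Planned | 100 v 100 | 0.28 |
| Allocated, pump-assisted v off-pump | 27 v 181 | 0.40 |
| Allocated, pump-assisted v on-pump | 27 v 128 | 0.42 |
| Observed MPO, pump-assisted v off-pump | 14 v 153 | 0.55 |
| Observed MPO, pump-assisted v on-pump | 14 v 102 | 0.56 |
| Observed MPO, off-pump v on-pump | 153 v 102 | 0.25 |

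The step from 0.28 to 0.40-0.42 is recruitment; the step to 0.55-0.56 is missing MPO. Under the further assumption of 80% power, the detectable difference is 0.40 SD at 100 v 100 and 0.78-0.80 SD for the observed pump-assisted contrasts. At a level of 0.0167, for three pairwise tests, these become 0.46 and 0.90-0.92 SD.

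**6. Observed MPO contrasts (means and SDs from Table 7, Welch intervals, ng/ml).**
- On-pump minus pump-assisted: 210.9 - 175.0 = 35.9; SE = √(138.7²/102 + 102.6²/14) = 30.7; 95% CI about -28 to 100.
- Pump-assisted minus off-pump: 175.0 - 96.2 = 78.8; SE = √(102.6²/14 + 75.3²/153) = 28.1; 95% CI about 19 to 139.
- On-pump minus off-pump: 210.9 - 96.2 = 114.7; SE = √(138.7²/102 + 75.3²/153) = 15.0; 95% CI about 85 to 144.

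**7. The null reading in the pump-assisted troponin section.** Table 21 prints model df 4, F 0.8 and eta-squared 0.45. Since F = (df_res/df_mod) × η²/(1 - η²), residual df = 0.8 × 4 × 0.55/0.45 = 3.9. Rounding of the printed values allows 3.6 to 4.2, so 4. Patients in the model: 4 + 4 + 1 = 9. As a check, F = 0.8 on 4 and 4 df gives p = 0.58, which agrees with the printed 0.6. With those df, a model would have to explain about 86% of the variance to reach p < 0.05.

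**The case against.** The strongest reply is that the plan contains no wrong figure. It says openly that no calculation was made, and a recruitment shortfall does not make a planning number false. This stands. A reader might infer that the stated size is an arithmetic error; the documents do not support that, because there are no inputs to recompute.

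The shortfall is also disclosed. Tables 1 to 3 give 27, Tables 2 and 3 set it beside the planned 100, and Table 25 shows 14 with MPO and warns of bias. This stands too, and the point is not one of concealment.

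It is tempting to say that the sample size shortfall doubled the interval width. That mixes enrolled with observed numbers. The planned 100s with the observed missingness would give about 52 v 85, or 0.35 SD, so missing MPO accounts for a good part of the loss. The SDs in Table 7 also differ (75.3, 138.7, 102.6), so the common-SD figures are only a guide.

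It is equally tempting to call the pump-assisted data worthless. The contrast with off-pump in step 6 excludes zero, so they are not.

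Finally, a reader might see the synopsis hypothesis and the primary hypothesis as directly opposed. The synopsis refers to ischemic-reperfusion injury, which Definitions ties to troponin I, while the primary hypothesis concerns MPO. The two may also be a null and an alternative. No equivalence margin or test is specified, so the documents show loose wording and not a planned equivalence claim.

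None of this rescues the sentence about untested hypotheses.

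**Conclusion.** The point holds in a limited form. The statement that no hypotheses will be tested is contradicted across the document and cannot justify the lack of a calculation. The size is unjustified for the tests run, and the pump-assisted group has 27% of its planned number by allocation and 14% on the primary endpoint. Off-pump v on-pump is at least as precise as planned. On-pump v pump-assisted is compatible with no difference or a large one.

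The practical harm lies in null readings. The summary that troponin after pump-assisted CABG is unrelated to MPO and bypass time rests on about 9 patients and a model explaining 45% of the variance.

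The precision figures depend on the assumptions in step 5 and do not describe the Kruskal-Wallis test. The Welch intervals are unadjusted, ignore skew, and treat missing MPO as ignorable, although the document itself classifies it as missing not at random.

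**What to change.** - In Sample Size Justification, delete the clause about untested hypotheses. Say that 300 (100 per group) was a planning number without a calculation, and keep it on record.
- Beside it, give the delivered numbers on the primary endpoint (153/102/14) and a confidence interval for each pairwise contrast.
- State the primary hypothesis once, as a difference in post-operative MPO.
- Label pump-assisted results as descriptive, and draw no conclusion of similarity or absence of dependence from them. Withdraw the summary under Table 21.
- Do not name a new main comparison now. The primary p-value (<.0001) is already printed, so choosing off-pump v on-pump would be driven by the results unless it is labelled post hoc.

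The cost is wording and a little analysis of existing data, with no new patients. The stated figures for pump-assisted CABG become less favourable.

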#### **Baseline Characteristics**

**Hypothesis: baseline characteristics are comparable between groups.**

Hypothesis testing:

- Normality test (Kolmogorov-Smirnov test, Shapiro-Wilk test)

Assessment of Myocardial Ischemic-Reperfusion Injury During Off- and On- Pump CABG (ClinicalTrials.gov Identifier: NCT03050489). Corresponding author: [name] [[contact]](mailto:[contact]) [contact]

Date of the document 06 December 2016

Group comparing:

Continuous variables

- Non-normal distribution: Kruskal-Wallis test with adjustment for multiple comparisons
- Normal distribution: t-test with multiple comparison adjustment

Nominal variables

- Chi-squared test/ Fisher's exact test

Baseline characteristics:

*Table 4 Baseline characteristics specification*

Characteristic	Variable name in database	Test
Age	Age	t-test
Gender	Sex	Chi-squared test/ exact Fisher's test
Syntax Score I	SS1	Kruskal-Wallis test
Syntax Score II	SS2	Kruskal-Wallis test
Euroscore II	EII	Kruskal-Wallis test
Charlson/ Deyo Index	ICD	Kruskal-Wallis test
Ejection Fraction	EFPreOp	Kruskal-Wallis test
End diastolic volume	EDVPreOp	Kruskal-Wallis test
End systolic volume	ESVPreOp	Kruskal-Wallis test

*Table 5 Baseline characteristics*

Variables	off-pump CABG (N=181)	on-pump CABG (N=128)	pump-assisted CABG (N=27)	P Value
Age in years				0.7836*
Mean±SD	63.5±7.3	63.6±7.1	64.3±8.9	
Min–Max	43.0–79.0	33.0–80.0	46.0–80.0	
Median (IQR)	63.0 (59.0–68.0)	64.0 (59.0–68.0)	66.0 (58.0–69.0)	
Syntax Score I				0.3667**
Nmiss (%)	1 (0.6)	2 (1.6)	1 (3.7)	

Variables	off-pump CABG (N=181)	on-pump CABG (N=128)	pump-assisted CABG (N=27)	P Value
Mean±SD	26.2±9.4	27.4±7.7	27.8±6.7	
Min–Max	2.0–61.0	10.0–52.5	14.0–43.5	
Median (IQR)	24.4 (22.0–31.8)	25.8 (22.0–31.5)	27.0 (22.0–33.0)	
Syntax Score II				0.6002
Nmiss (%)	1 (0.6)	2 (1.6)	1 (3.7)	
Mean±SD	41.7±11.6	40.9±12.5	43.5±11.6	
Min–Max	8.1–68.0	3.7–68.3	24.6–67.6	
Median (IQR)	41.4 (32.7–50.8)	42.3 (31.1–49.9)	43.5 (34.5–53.6)	
EuroScore I				0.3137
Mean±SD	1.4±1.3	1.3±1.0	1.4±1.4	
Min–Max	0.5–10.8	0.5–5.5	0.5–6.7	
Median (IQR)	1.0 (0.7–1.5)	1.0 (0.6–1.5)	0.8 (0.6–1.4)	
Index Charlson/Deyo				0.1141
Nmiss (%)	1 (0.6)			
Mean±SD	5.4±2.0	5.0±1.8	4.9±2.0	
Min–Max	1.0–11.0	0.0–10.0	2.0–10.0	
Median (IQR)	5.0 (4.0–7.0)	5.0 (4.0–6.0)	5.0 (4.0–6.0)	
Ejection Fraction before operation				0.9090
Nmiss (%)	1 (0.6)	2 (1.6)		
Mean±SD	60.2±10.4	60.9±8.5	58.4±11.7	
Min–Max	30.0–85.0	28.0–85.0	30.0–72.0	
Median (IQR)	62.0 (55.0–67.0)	62.0 (59.0–66.0)	63.0 (55.0–65.0)	
End diastolic volume				0.2187
Nmiss (%)	5 (2.8)	5 (3.9)		
Mean±SD	115.7±41.5	115.7±34.8	131.1±53.6	
Min–Max	11.0–270.0	44.0–224.0	81.0–367.0	
Median (IQR)	109.0 (91.0–131.5)	114.0 (90.0–139.0)	121.0 (101.0–141.0)	
End Systolic Volume				0.4178
Nmiss (%)	5 (2.8)	5 (3.9)		
Mean±SD	48.0±28.0	46.8±23.0	50.5±20.7	
Min–Max	11.0–178.0	12.0–138.0	23.0–107.0	

Assessment of Myocardial Ischemic-Reperfusion Injury During Off- and On- Pump CABG

(ClinicalTrials.gov Identifier: NCT03050489). Corresponding author: [name]

[[contact]](mailto:[contact]) [contact]

Date of the document 06 December 2016

Variables	off-pump CABG (N=181)	on-pump CABG (N=128)	pump-assisted CABG (N=27)	P Value
Median (IQR)	40.5 (31.0–55.0)	43.0 (32.0–54.0)	44.0 (38.0–55.0)	
Gender				0.6268***
Male	142 (78.5)	95 (74.2)	20 (74.1)	
Female	39 (21.5)	33 (25.8)	7 (25.9)	

\* ANOVA, \*\* Kruskal-Wallis test, Nmiss – number of missing values, SD – standard deviation, IQR – interquartile range, \*\*\* - Chi-squared test, CABG – coronary artery bypass grafting

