### **Patients allocation**

Patients were allocated into one of three groups of treatment by Heart Team. Patients consecutively admitted in the Department of Cardiac Surgery #1 and #2. All patients who admitted in the Department of Cardiac Surgery #1 allocated into off-pump CABG group. Patients who admitted in the Department of Cardiac Surgery #2 allocated into off-pump CABG group, on-pump CABG group (when have proximal lesions of RCA or LCx), off-pump CABG group (when have more distal lesion of coronary arteries) or pump-assisted CABG group (when have difusse coronary artery lesions). Heart Team includes three or more cardiac surgeons who performs off-pump, on-pump or pump-assisted CABG more than 10 years, two or more interventional cardiologists, one neurologist, two or more anesthesiologist, two or more reanimatologist, one perfusologist and two cardiologist. After debating patients were alocated into one of threy groups for elective CABG.

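### Baseline comparability of the non-randomised groups is addressed only by low-powered significance tests, and no planned model adjusts for the Table 5 variables or the allocation factors

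*Combined protocol and SAP*

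**What the plan says.** Under Patients allocation: "Patients were allocated into one of three groups of treatment by Heart Team". Every patient admitted to Department #1 went to off-pump surgery. In Department #2 the choice followed whether lesions were proximal, more distal or diffuse.

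Under Baseline Characteristics the plan states "Hypothesis: baseline characteristics are comparable between groups". The tools it lists are normality tests, then t-tests, "Non-normal distribution: Kruskal-Wallis test with adjustment for multiple comparisons", and chi-squared or Fisher tests. Table 5 gives one three-group p-value per variable, all above 0.11, with no standardised difference and no margin. Neither department nor lesion pattern is tabulated.

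Baseline MPO is not in Table 4 or Table 5. It appears under Primary endpoint analysis, in the Table 7 row "MPO before CABG", with a Kruskal-Wallis p of 0.2904. Postoperative MPO, the primary endpoint, is compared by the same unadjusted test. The Secondary Endpoint Analysis names Kruskal-Wallis for continuous outcomes, and the troponin I group comparisons follow in Table 30.

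The ANCOVAs for MPO (Table 10) and first-day troponin I (Table 13) include log baseline MPO. Their other covariates are log postoperative MPO (troponin model), number of complications (MPO model), cross-clamp time, bypass time and operation time.

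The Sample Size Justification says "no statistical hypotheses will be tested, sample size calculation was not conducted for this study".

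**The concern.** A non-significant test does not show that groups are alike, least of all when one group is small. Here the groups were formed by clinical judgement on anatomy and by department, so pre-operative differences are to be expected and can bias the comparison of MPO and troponin I. If Table 5 is read as settling the matter, no reason remains to adjust for what it shows, and the planned models do not. The risk is greatest for contrasts with the pump-assisted group, where real imbalance is easiest to miss.

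**Working it through.** **Inputs.** Means, SDs and missing counts come from Tables 5 and 7. Baseline MPO was measured in 181−34 = 147 off-pump, 128−21 = 107 on-pump and 27−9 = 18 pump-assisted patients. The plan states no alpha or power; I assume a two-sided 0.05.

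**The plan's figure.** The Kruskal-Wallis p of 0.2904 cannot be reproduced without patient data. A one-way ANOVA from the Table 7 summaries gives F=1.17, p=0.312, which is consistent with it.

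**Standardised differences**, SMD = difference in means / sqrt((s1² + s2²)/2):

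- Charlson/Deyo (p=0.1141): off-pump v on-pump (5.4−5.0)/sqrt((2.0²+1.8²)/2) = 0.4/1.90 = 0.21; off-pump v pump-assisted 0.5/2.0 = 0.25.
- End diastolic volume (p=0.2187): pump-assisted v off-pump (131.1−115.7)/sqrt((53.6²+41.5²)/2) = 15.4/47.9 = 0.32; v on-pump 15.4/45.2 = 0.34.
- Baseline MPO, on-pump v pump-assisted (three-group p=0.2904): (39.9−29.2)/sqrt((30.6²+14.8²)/2) = 10.7/24.04 = 0.445, approximate 95% CI −0.06 to 0.95. The other two pairs give 0.26 (off-pump v pump-assisted) and 0.13 (off-pump v on-pump).

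**How stable are these?**

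- End diastolic volume: the pump-assisted maximum is 367. If the blank missing count means n=27, removing it gives a mean of (27×131.1−367)/26 = 122.0. The sum of squares becomes 26×53.6² − (367−131.1)²×27/26 = 16,908, so the SD is sqrt(16,908/25) = 26.0. The SMDs fall to 6.3/34.6 = 0.18 and 6.3/30.7 = 0.21.
- Baseline MPO: with the n-weighted pooled SD the value is 10.7/28.9 = 0.37. On the log scale, approximated from quartiles or by matching lognormal moments, it is about 0.11 to 0.33. The medians are 31.0 and 29.0.

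**What the tests can detect.** The observed pairwise SMD that just reaches p<0.05 is 1.96 × sqrt(1/n1 + 1/n2):

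| Groups | Just significant | Detectable with 80% power |
|---|---|---|
| 27 v 181 | 0.40 | 0.58 |
| 27 v 128 | 0.42 | 0.59 |
| 18 v 107 | 0.50 | 0.71 |

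The last column replaces 1.96 by 1.96+0.84. These are unadjusted two-group thresholds, whereas the planned test is a three-group rank test. So the Kruskal-Wallis test was also simulated (4000 runs, normal data, pump-assisted group shifted by 0.45 SD). Its power is about 49% with 181/128/27, 32% with 147/107/18, and 90% with the planned 100 per group.

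**What the models contain.** No Table 5 variable, department or lesion pattern appears in any model specification from Table 8 onwards. Complications and the three durations arise after allocation, so they do not control pre-operative confounding.

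**The case against.** Several points on the other side stand.

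- A reader might infer that the plan has a rule declaring the groups comparable when p exceeds 0.05. It has none. It states a hypothesis and prints p-values, never writes that the groups are comparable, and ties no adjustment to a p-value. Baseline MPO had p=0.29 and was adjusted for all the same.
- A reader might also infer that a 0.45 SD imbalance in baseline MPO was missed because the smallest group has 27 patients. That does not hold. The relevant number is 18, and with 27 v 128 an observed 0.45 would pass the 0.42 threshold. The figure is the largest of three contrasts, on raw means of a skewed marker with very unequal SDs. A Welch test for that pair gives p=0.024 (equal-variance p=0.15), so the choice of a three-group rank test matters as well as sample size.
- Baseline MPO imbalance is not left uncorrected: the ANCOVAs include it, and the synopsis names ANOVA/ANCOVA for MPO and troponin I.
- The end diastolic volume gap leans on one value, and the Charlson/Deyo medians are 5.0 in all three groups.
- The study calls itself exploratory.

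These points reduce the size of the finding. They do not supply adjustment for any other pre-operative variable, and they leave the primary Kruskal-Wallis test unadjusted.

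**Conclusion.** The point holds in limited form. Comparability of groups formed by department and lesion pattern is examined only by tests with little power against the pump-assisted group. Non-significant results coexist with standardised differences of roughly 0.2 to 0.3. For baseline MPO, the interval of −0.06 to 0.95 excludes neither balance nor a large imbalance. The consequential gap is that the primary MPO test and the troponin I group tests are unadjusted, while the models add only baseline MPO among pre-operative variables.

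It would go too far to say that adjustment would overturn the off-pump v on-pump MPO difference. Postoperative medians are 66.5 and 184.3, and nothing in the documents suggests confounding of that size. The exposure is mainly in the pump-assisted contrasts and troponin I.

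The conclusion rests on the printed summaries, the assumed two-sided 0.05 and, for the end diastolic volume sensitivity, n=27.

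**What to change.** 1. Drop the comparability hypothesis. Report pairwise standardised differences for the Table 5 variables and baseline MPO.
2. Make the between-group MPO and troponin I comparison a model of the log outcome on group and log baseline MPO plus a short list of Table 5 variables, for example age, Syntax score, Charlson/Deyo, and ejection fraction or end diastolic volume. Leave complications and the operative durations out of this model.
3. Choose that list on clinical grounds, not by a cut-off on p or SMD. With 27 v 128 the standard error of an SMD is about sqrt(1/27+1/128) = 0.21, so a threshold of 0.1 would be crossed by chance about 64% of the time.
4. Add lesion pattern if it was recorded; no such variable is listed in the variable tables. Add a sensitivity analysis restricted to Department #2. Department #1 contributes only off-pump patients, so restriction handles department better than a covariate alone.

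The cost is a few degrees of freedom and wider intervals for the pump-assisted contrasts. Only 14 of those patients have a postoperative MPO value, so these contrasts should be described as imprecise. The standardised differences need only figures already printed. If lesion pattern largely determines the operation, overlap between groups may be thin, and the report should say so.
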